#### Table 2Estimands

Estimand			Att	ributes		
	Treatment	Population	Endpoint (Variable)	Intercurrent ev		
				Description	Handling strategy	Summary measure
Primary	One dose of the investigational mRNA-CR vaccine.	Healthy adults, 18 to 49 years of age, who were primed and received booster dose(s) of an authorized or licensed mRNA COVID -19 vaccine with the last booster dose administered at least 6 months or more prior to screening, inclusive at the time of the vaccination.	
 
Solicited administration site events and systemic events with onset during the 7-day follow-up period after study vaccine administration (day of study vaccine administration and 6 subsequent days);
 
Unsolicited AEs with onset during the 30- day follow-up period after study vaccine administration (day of study vaccine administration and 29 subsequent days);
 
Any hematological and biochemical laboratory abnormality during
 
	
 
Study vaccination not administered as per protocol
 
Any intercurrent conditions or any concomitant medication/vaccination that may confound the safety investigational product causality assessment prior to D31
 
	The data collected from all participants receiving one dose of investigational vaccine will be used regardless of whether the intercurrent event occurs (Treatment policy) Rationale: treatment policy strategy is used as all data will contribute to evaluate the safety parameters.	Proportion of participants in each treatment group for each endpoint

Estimand			Att	ribut	es		
	Treatment	Population	Endpoint (Variable)	Intercurrent events (ICEs)			
					Description	Handling strategy	Summary measure
Secondary	One dose of the investigational mRNA-CR vaccine.	Healthy adults, 18 to 49 years of age, who were primed and received booster dose(s) of an authorized or licensed mRNA COVID -19 vaccine with the last booster dose administered at least 6 months or more prior to	the 15-day follow-up period after study vaccine administration (day of study vaccine administration and 14 subsequent days); • MAAEs; SAEs; AESIs up to D31. MAAEs; SAEs; AESIs from Day 1 up to study conclusion (M6).	•	Study vaccination not administered as per protocol Any intercurrent conditions or any concomitant medication/vaccination that may confound the safety investigational product causality assessment prior to M6	The data collected from all participants receiving one dose of investigational vaccine will be used regardless of whether the intercurrent event occurs (Treatment policy) Rationale: treatment policy strategy is used as all data will contribute to evaluate the safety parameters	Proportion of participants in each treatment group for each endpoint

Estimand			Att	ribut	es		
	Treatment	Population	Endpoint (Variable)	ble) Intercurrent events (ICEs)		- Summent	
					Description	Handling strategy	Summary measure
		inclusive at the time of the vaccination.					
Secondary	One dose of the investigational mRNA-CR vaccine.	Healthy adults, 18 to 49 years of age, who were primed and received booster dose(s) of an authorized or licensed mRNA COVID -19 vaccine with the last booster dose administered at least 6 months or more prior to screening, inclusive at the time of the vaccination.	Neutralizing titer against pseudovirus bearing S protein from vaccine encoded SARS-CoV-2 and WT strains at each collection timepoint (D1, D15, D31, M6).	•	Study vaccination not administered as per protocol A condition that has the capability of altering the immune response (e.g., HIV, lymphoma, COVID) to the study intervention or is confirmed to have an alteration of the participant's initial immune status Major protocol deviations including out of visit window blood samples.	The Hypothetical strategy will be used. The data after the ICEs will be ignored. Rationale: To estimate the treatment effect on participants who are dosed and have no major protocol deviations.	Geometric Mean Titer for each treatment group

Estimand		Attributes							
	Treatment	Population	Endpoint (Variable)		Intercurrent ev	vents (ICEs)	Summani		
					Description	Handling strategy	Summary measure		
Secondary	One dose of the investigational mRNA-CR vaccine.	Healthy adults, 18 to 49 years of age, who were primed and received booster dose(s) of an authorized or licensed mRNA COVID -19 vaccine with the last booster dose administered at least 6 months or more prior to screening, inclusive at the time of the vaccination.	GMR from baseline (D1) of neutralizing titer against pseudovirus bearing S protein from vaccine encoded SARS-CoV-2 and WT strains at each collection timepoint.	•	Study vaccination not administered as per protocol A condition that has the capability of altering the immune response (e.g. HIV, lymphoma, COVID) to the study intervention or is confirmed to have an alteration of the participant's initial immune status Major protocol deviations including out of visit window blood samples.	The Hypothetical strategy will be used. The data after the ICEs will be ignored. Rationale: To estimate the treatment effect on participants who are dosed and have no major protocol deviations.	Geometric Mean Ratio for each treatment group		
Secondary	One dose of the investigational mRNA-CR vaccine.	Healthy adults, 18 to 49 years of age, who were primed and received booster	Vaccine response rate based on neutralizing titers against vaccine encoded SARS-CoV-2 and WT	•	Study vaccination not administered as per protocol A condition that has the capability of altering the immune	The Hypothetical strategy will be used. The data after the ICEs will be ignored. Rationale: To estimate the treatment effect on participants	Vaccine response rate in each treatment group for each endpoint		

Attributes							
Treatment	Population	Population Endpoint (Variable)		Intercurrent events (ICEs)			
				Description	Handling strategy	Summary measure	
	dose(s) of an authorized or licensed mRNA COVID -19 vaccine with the last booster dose administer at least 6 months or more prior to screening, inclusive at the time of the vaccination.	strains at each collection timepoint.	•	response (e.g. HIV, lymphoma, COVID) to the study intervention or is confirmed to have an alteration of the participant's initial immune status Major protocol deviations including out of visit window blood samples.	who are dosed and have no major protocol deviations.		
	Treatment	dose(s) of an authorized or licensed mRNA COVID -19 vaccine with the last booster dose administer at least 6 months or more prior to screening, inclusive at the time of the	TreatmentPopulationEndpoint (Variable)dose(s) of an authorized or licensed mRNA COVID -19 vaccine with the last booster dose administer at least 6 months or more prior to screening, inclusive at the time of thestrains at each collection timepoint.	Treatment       Population       Endpoint (Variable)         dose(s) of an authorized or licensed mRNA COVID -19 vaccine with the last booster dose administer at least 6 months or more prior to screening, inclusive at the time of the       strains at each collection timepoint.	Treatment         Population         Endpoint (Variable)         Intercurrent endpoint (Variable)           dose(s) of an authorized or licensed mRNA COVID -19         strains at each collection timepoint.         response (e.g. HIV, lymphoma, COVID) to the study intervention or is confirmed to have an alteration of the participant's initial immune status           iast booster dose administer at least 6 months or more prior to screening, inclusive at the time of the         Major protocol deviations including out of visit window blood samples.	Treatment         Population         Endpoint (Variable)         Intercurrent events (ICEs)           dose(s) of an authorized or licensed mRNA COVID -19 vaccine with the last booster dose administer at least 6 months or more prior to screening, inclusive at the time of the         strains at each collection timepoint.         response (e.g. HIV, lymphoma, COVID) to the study intervention or is confirmed to have an alteration of the participant's initial immune status         who are dosed and have no major protocol deviations.	

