# 9.3. Analysis sets

#### Table 17Analysis sets

Analysis set	Description
Screened	All participants who were screened for eligibility.
Enrolled	Participants who completed the informed consent process, meet screening/eligibility criteria and undergone an invasive procedure. Note: screening failures (who never passed screening even if re-screened) and participants screened but never enrolled into the study (Met eligibility but not needed) are excluded from the Enrolled analysis set as they did not enter the study.
Exposed	All participants who received the dose of the study intervention. Analysis per group using the enrolled set based on the administered intervention.
Per Protocol	All eligible participants who received dose of study intervention as per protocol, without intercurrent conditions that may interfere with immunogenicity and without prohibited concomitant medication/vaccination, and who have values for pre-dose and post-dose neutralizing antibody titer against pseudovirus bearing S protein data for the relevant timepoint, and without major protocol deviations. The PPS for immunogenicity will be defined by time point.
Solicited Safety	All participants who received the dose of the study intervention (Exposed Set) who have reported the presence or absence of any solicited AE at least once.

AE: Adverse event; D: Day; S: Spike; PPS: Per Protocol Set

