### 9.3.1. Criteria for elimination from analysis

If a participant meets one of the criteria mentioned below, they may be eliminated from per protocol analysis.

- Receive any of the medications/products/vaccines listed in Section 5.2.2.
- Incur an intercurrent medical condition that could alter their immune response (i.e., varicella, HIV, lymphoma) or are confirmed to have an alteration of their initial immune status.
- Major protocol deviation(s) linked to the eligibility criteria (Section 5.1 and Section 5.2).
- Study intervention not administered as specified by the protocol.
- Failure to comply with the post-dose immunogenicity blood sampling schedule at a given timepoint (Section 1.3).
- Other major protocol deviation during vaccination phase that led to exclusion.

The SAP will provide a complete list of criteria for elimination from PP analyses.

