# 3. ANALYSIS SETS

## 3.1. Definition

#### Table 5Analysis sets

Analysis set	Description	Analyses Evaluated
Screened	All participants who were screened for eligibility.	Study Population
Enrolled	Participants who completed the informed consent process,	Study Population
	meet screening/eligibility criteria and undergone an invasive	
	procedure.	
	Note: screening failures (who never passed screening even if	
	re-screened) and participants screened but never enrolled	
	into the study (Met eligibility but not needed) are excluded	
	from the Enrolled analysis set as they did not enter the study.	
Exposed	All participants who received the dose of the study	Safety excluding solicited AE
	intervention. Analysis per group using the enrolled set based	
	on the administered intervention.	
Per Protocol	All eligible participants who received dose of study	Immunogenicity
	intervention as per protocol, without intercurrent conditions	
	that may interfere with immunogenicity and without prohibited	
	concomitant medication/vaccination, and who have values for	
	pre-dose and post-dose neutralizing titer against pseudovirus	
	bearing BA. 5 S protein data for the relevant timepoint, and	
	without major protocol deviations.	
	The PPS for immunogenicity will be defined by time point.	
Solicited	All participants who received the dose of the study	Safety
Safety	intervention (Exposed Set) who have reported the presence	
	or absence of any solicited AE at least once.	

AE: Adverse event; D: Day; S: Spike; PPS: Per Protocol Set

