# 4. STATISTICAL ANALYSES

## 4.1. General Considerations

Standard data derivation rules and statistical methods are described in section 6.2.

Unless otherwise specified, analysis of safety endpoints will be performed on the Exposed Set. The primary analysis of the immunogenicity endpoints will be performed on the Per Protocol Set (PPS).

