## 6. SUPPORTING DOCUMENTATION

## 6.1. Appendix 1 Study Population Analyses

## 6.1.1. Participant Disposition

Participant disposition will be summarized by treatment and overall using descriptive statistics:

• Number of participants screened, randomised, vaccinated including withdrawal reasons will be tabulated.

Withdrawal status will be summarized using descriptive statistics:

- The number of participants exposed as well as the number of participants excluded from PPS analyses will be tabulated at D15, D31, and M6.
- The numbers of withdrawn participants will be tabulated according to the reason for withdrawal.

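### SAP Table 2 treats an out-of-window blood sample as an intercurrent event after which data are ignored, with no limit to the affected visit, and this is not reconciled with the time-point-specific Per Protocol Set

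*SAP*

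**What the plan says.** **Estimands.** SAP Table 2 has three secondary immunogenicity estimands: neutralizing GMT, GMR from baseline, and vaccine response rate. Each lists the same three intercurrent events. Two are vaccination not given per protocol and a condition able to alter the immune response. The third is "Major protocol deviations including out of visit window blood samples". One handling rule covers all three: "The Hypothetical strategy will be used. The data after the ICEs will be ignored". It carries no visit limit.

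**Analysis set.** SAP Section 4.1 puts the primary immunogenicity analysis on the PPS. SAP Table 5 says "The PPS for immunogenicity will be defined by time point". Protocol Table 17 has the same rule, placed directly after a general condition: "and without major protocol deviations. The PPS for immunogenicity will be defined by time point". Protocol Section 9.3.1 lists, among the reasons for which a participant may be eliminated, "Failure to comply with the post-dose immunogenicity blood sampling schedule at a given timepoint". SAP Section 6.1.1 reports exclusions by visit: "the number of participants excluded from PPS analyses will be tabulated at D15, D31, and M6".

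**Windows.** Protocol Table 2 allows 12-16 days after Visit 1 for Day 15, 27-33 for Day 31 and 173-187 for Month 6.

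**The concern.** The other two intercurrent events can plausibly change every later titre, so ignoring later data is coherent for them. A draw on the wrong day is different. It changes which day one measurement represents and has no effect on the titre at the next visit. Applying the same rule to it removes good later samples for a reason unrelated to them.

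Two programmers could therefore build different Day 31 and Month 6 datasets from the same SAP, one from Table 2 and one from the time-point PPS. Groups are small (18 vaccinees, 16 planned evaluable), so a few carried-forward exclusions would be visible in the confidence intervals. Protocol Section 9.3.1 leaves the complete list of elimination criteria to the SAP, but the SAP text contains no such list. Table 2 is the only place in the SAP that deals with out-of-window samples explicitly.

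**Working it through.** **1. The texts side by side, for a participant with a late Day 15 draw and in-window Day 31 and Month 6 draws.**

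| Rule | Day 31 and Month 6 titres |
|---|---|
| SAP Table 2, as written | Ignored, as data after the event |
| PPS by time point (SAP Table 5, Protocol Table 17) | Kept |
| General major-deviation condition in the same PPS definition | Unclear: no time limit, and SAP Table 2 classes the late draw as a major deviation |
| Protocol 9.3.1 | Sampling failure is tied to a time point, but elimination is only permitted, and its reach is not stated |

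One such participant can lose up to two later valid samples. Under any of these rules Day 15 itself is not where they differ, provided the mistimed sample is excluded there.

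**2. The plan's own precision figure.** Inputs from SAP Section 5: n = 16 evaluable, SD 0.45 on the log10 scale, two-sided 95% CI. The ratio of upper limit to GMR is 10^(t(0.975, n-1) x SD / sqrt(n)).

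n = 16: 10^(2.131 x 0.45 / 4) = 10^0.240 = 1.737. The stated 1.74 reproduces.

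**3. Losing 1, 2 or 3 of the 16 at a later visit (assumed counts), same formula.**

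- n = 15: 1.775
- n = 14: 1.819
- n = 13: 1.870

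Relative to 1.737 the factor is 1.775/1.737 = 1.02 to 1.870/1.737 = 1.08 times as large, so about 2% to 8% wider.

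**4. The same question from an assumed rate.** Let q be the chance of an out-of-window draw at each post-dose visit, independent across visits, with 18 vaccinees and no other losses. In both columns the mistimed sample itself is excluded. Expected n at Month 6 is 18(1-q) if exclusion is visit-specific and 18(1-q)^3 if it carries forward. The factor uses n rounded to a whole number.

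| q | n, visit-specific | n, carried forward | in-window Month 6 samples lost | factor, visit-specific | factor, carried forward |
|---|---|---|---|---|---|
| 2% | 17.64 | 16.94 | 0.70 | 1.67 | 1.70 |
| 5% | 17.10 | 15.43 | 1.67 | 1.70 | 1.78 |
| 10% | 16.20 | 13.12 | 3.08 | 1.74 | 1.87 |
| 15% | 15.30 | 11.05 | 4.25 | 1.78 | 2.01 |

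At Day 31 the corresponding loss is 18q(1-q), about 0.4 to 2.3 samples per group over the same range.

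**The case against.** The strongest reply is that the PPS, not the estimand table, builds the datasets. SAP Section 4.3.2.1 runs the secondary immunogenicity analyses on the PPS and restricts the models to it, and the PPS is set by time point. A programmer following those sections can keep an in-window Day 31 sample after a late Day 15 draw. This stands. A reader might infer from Table 2 that the plan definitely discards such samples; the documents do not support that.

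A reader might also infer that Protocol 9.3.1 and SAP Table 5 state the opposite of Table 2. That goes too far as well, because Table 5 also contains the unlimited major-deviation condition and 9.3.1 only permits elimination. The texts are unreconciled rather than opposed.

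A third tempting reading is that Table 2 keeps the late sample itself, since it is not after the event. That is strained: the rationale in the same row targets participants without major deviations, and 9.3.1 lists sampling-schedule failure separately.

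Table 2 defines its variables at each collection time point, so it can be read visit by visit. That reading is available, but then nothing at that visit follows the mistimed draw and the instruction about later data has no work to do for this event. The text does not settle it.

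On size, n = 16 already allows for 10% unevaluable (18 x 0.9 = 16.2), which may include schedule failures, so subtracting from 16 may count some losses twice. SAP Section 4.3.2.1 also plans an Exposed Set sensitivity analysis if more than 10% of participants with Day 15 BA.5 data are eliminated from any PPS in any group. With 18 such participants, two suffice (2/18 = 11.1%) and one does not (1/18 = 5.6%). That limits the consequence, but it does not tell the programmer which PPS to build.

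**Conclusion.** The point holds as an unreconciled conflict between the estimand table and the analysis set. Table 2, as written, states a rule that fits this event badly and could remove valid Day 31 and Month 6 titres. Whether it does depends on which section the programmer follows, and on how the general major-deviation condition is read.

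Importance is low. The study is descriptive, with no hypothesis test to invalidate. The precision figures are illustrations only: they rest on assumed counts or rates, independence across visits in the rate-based table, and the plan's SD of 0.45. Within those assumptions the effect runs from negligible at a 2% out-of-window rate to clearly visible at Month 6 at 10% or more.

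**What to change.** In the SAP:

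1. Remove out-of-window blood samples from the intercurrent-event list in the three secondary immunogenicity estimands of Table 2.
2. State in Table 5 that such a sample is excluded from the PPS at its own time point only.
3. State that it does not trigger the general major-deviation exclusion at other time points.

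The cost is wording in an SAP amendment. It needs no new data and no change to visits, and it matches the by-visit reporting of PPS exclusions already planned. It should be settled before the Day 31 and Month 6 datasets are built.

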## 1.2. Study Design

This is an exploratory, FTIH, observer-blind, randomized, controlled study.

In part A of this study, three doses  $(10 \ \mu g, 30 \ \mu g, and 100 \ \mu g)$  of the mRNA-CR-04 vaccine will be evaluated. Approximately 72 eligible healthy adults, 18 to 49 years, inclusive, will be enrolled with 24 participants per group (Group 1, Group 2 and Group 3). Within each group, participants will be randomly assigned in a 3:1 ratio:

- 18 participants will receive the investigational mRNA-CR-04 vaccine and
- 6 participants will receive a saline placebo (sodium chloride [NaCl] isotonic solution [0.9%]).

In Part B of the study, 2 doses (3  $\mu$ g and 10  $\mu$ g) of the mRNA-CR-04 vaccine will be evaluated. Approximately 42 eligible healthy adults, 18 to 49 years, inclusive, will be enrolled in Part B and will be randomly assigned in a 3:3:1 ratio:

[figure not shown]
- 18 participants will receive 3 µg of the investigational mRNA-CR-04 vaccine and
- 18 participants will receive 10 µg of the investigational mRNA-CR-04 vaccine and
- 6 participants will receive a saline placebo (sodium chloride [NaCl] isotonic solution [0.9%]).

Study duration for all the participants will be approximately 6 months, and they will be evaluated for safety, reactogenicity and immunogenicity. Safety monitoring and safety data review will be performed by a GSK SRT (blinded data review until Part A Day 15 interim analysis, unblinded review subsequently) and a GSK iSRC (unblinded data review).

Overview of the study design is presented in Figure 1.

Study design overview

- CMI: Cell-mediated immunity; D: Day; M: Month; mRNA: mRNA-CR-04 vaccine; n: Number of participants; SE: Solicited events; TC: Telephone call; V: Visit.
- \* TC1 D2 only for sentinel participants in each group. \*\* The first participant is to be enrolled in Group 1. In addition to the defined intervals between doses within each group, an interval of at least 60 minutes will be maintained between the vaccination of sentinel participants across Group 1 and Group 2. \*\*\* TC1 review will be performed by the SRT on blinded data.

Table 3 and Table 4 describe the Part A and Part B study groups, interventions, and blinding, respectively.

Study	Number of	Age (Min-	Study intervention(s)	/vaccine(s) mode of	Blinding
groups	participants	Max years of age)	adminis	Screening→Visit5	
Croup 1	18	18 – 49	mRNA-CR-04 vaccine 10 μg	Intramuscular injection into the deltoid muscle,	Observer-blind
Group 1	6	18 – 49	Saline placebo (NaCl [0.9%])	preferably of the non- dominant arm.	Observer-billio
Group 2	18	18 – 49	mRNA-CR-04 vaccine 30 µg	Intramuscular injection into the deltoid muscle,	Observer-blind
Gloup 2	6	18 – 49	Saline placebo (NaCl [0.9%])	preferably of the non- dominant arm.	Observer-billio
Group 3	18	18 – 49	mRNA-CR-04 vaccine 100 μg	Intramuscular injection into the deltoid muscle,	Observer blind
Group 5	Group 3		preferably of the non- dominant arm.	Observer-blind	

 Table 3
 Part A study groups, intervention and blinding

NaCl: Sodium chloride.

Table 4Part B study groups, interventions, and blinding

Study groups	Number of participants	Age (Min- Max years of age)		Study intervention(s)/vaccine(s) mode of administration	
Part B 3 µg	18	18 – 49	mRNA-CR-04 vaccine 3 µg	Intramuscular injection into the deltoid muscle, preferably of the non-dominant arm.	Observer-blind (except sponsor)
Part B 10 µg	18	18 – 49	mRNA-CR-04 vaccine 10 μg	Intramuscular injection into the deltoid muscle, preferably of the non-dominant arm.	Observer-blind (except sponsor)
Part B Placebo	6	18 – 49	Saline placebo (NaCl [0.9%])	Intramuscular injection into the deltoid muscle, preferably of the non-dominant arm.	Observer-blind (except sponsor)

NaCI: Sodium chloride.

